| Malignancy (excluding dysplasia) (score 2 if > 1 site)   |  1  2 |      |       |  |  |                   |                            |                                 |                            |                         |  |   |                            |   |                            |  |   |  |                            |                     |                            |              |  |  |                            |                              |                            |    |  |   |                            |                  |  |   |                            |  |                            |                |                            |                                 |                            |                                     |                            |                       |  |                                  |                            |   |   |  |                            |  |                            |  |                            |                            |  |                           |                            |                                |                            |   |   |   |                            |                         |  |   |   |                          |                            |                     |                            |  |                            |                        |  |                            |                            |  |                            |   |                            |                                     |   |               |                            |             |  |                           |                            |  |                            |   |                            |                                  |                            |   |                            |  |   |

### 13.7. CLASI

BOS161721-02      Subject: \_\_\_\_\_ Visit: \_\_\_\_\_ Date: \_\_\_\_-\_\_\_\_-20\_\_\_\_  
 Day   Month   Year

#### Cutaneous LE Disease Area and Severity Index (CLASI)

Select the score in each anatomical location that describes the most severely affected cutaneous lupus-associated lesion

| Anatomical Location       | activity   |  | damage                         |  | Anatomical Location       |
|---------------------------|--|--|--------------------------------|--|---------------------------|
|                           | Erythema   | Scale/
Hypertrophy                                | Dyspigmentation                | Scarring/
Atrophy/
Panniculitis  |                           |
|                           | 0-absent
1-pink; faint erythema
2-red;
3-dark red;
purple/violaceous/
crusted/hemorrhagic | 0-absent;
1-scale
2-verrucous/
hypertrophic | 0-absent,
1-dyspigmentation | 0 – absent
1 – scarring
2 – severely
atrophic scarring
or panniculitis |                           |
| Scalp                     |  |  |                                | See below  | Scalp                     |
| Ears                      |  |  |                                |  | Ears                      |
| Nose (incl. malar area)   |  |  |                                |  | Nose (incl. malar area)   |
| Rest of the face          |  |  |                                |  | Rest of the face          |
| V-area neck (frontal)     |  |  |                                |  | V-area neck (frontal)     |
| Post. Neck &/or shoulders |  |  |                                |  | Post. Neck &/or shoulders |
| Chest                     |  |  |                                |  | Chest                     |
| Abdomen                   |  |  |                                |  | Abdomen                   |
| Back, buttocks            |  |  |                                |  | Back, buttocks            |
| Arms                      |  |  |                                |  | Arms                      |
| Hands                     |  |  |                                |  | Hands                     |
| Legs                      |  |  |                                |  | Legs                      |
| Feet                      |  |  |                                |  | Feet                      |

#### Mucous membrane

#### Dyspigmentation

|   |  |
|---|--|
| Mucous membrane lesions (examine if patient confirms involvement) | Report duration of dyspigmentation after active lesions have resolved (verbal report by patient – tick appropriate box)  |
| 0-absent;
1-lesion or ulceration                               |  Dyspigmentation usually lasts less than 12 months (dyspigmentation score above remains)
 Dyspigmentation usually lasts at least 12 months (dyspigmentation score is doubled) |
|   |  |

#### Alopecia

|  |   |   |
|--|---|---|
| Recent Hair loss
(within the last 30 days / as reported by patient)   |   | NB: if scarring and non-scarring aspects seem to coexist in one lesion, please score both |
| Divide the scalp into four quadrants as shown. The dividing line between right and left is the midline. The dividing line between frontal and occipital is the line connecting the highest points of the ear lobe. A quadrant is considered affected if there is a lesion within the quadrant. |   |   |
| Alopecia (clinically not obviously scarred)  | Scarring of the scalp (judged clinically)   |   |
| 0-absent
1-diffuse; non-inflammatory
2-focal or patchy in one quadrant;
3-focal or patchy in more than one quadrant   | 0- absent
3- in one quadrant
4- two quadrants
5- three quadrants
6- affects the whole skull |   |

#### Total Activity Score

(For the activity score please add up the scores of the left side i.e. for Erythema, Scale/Hypertrophy, Mucous membrane involvement and Alopecia)

#### Total Damage Score

(For the damage score, please add up the scores of the right side, i.e. for Dyspigmentation, Scarring/Atrophy/Panniculitis and Scarring of the Scalp)

Sponsor: Boston Pharmaceuticals, Inc.

Protocol Number: BOS161721-02

SAP Version and Date: Version 3.0, 13Nov2020

13.8. **CCI**

13.8.1. **CCI**

**CCI**

Sponsor: Boston Pharmaceuticals, Inc.

Protocol Number: BOS161721-02

SAP Version and Date: Version 3.0, 13Nov2020

**CCI**

Sponsor: Boston Pharmaceuticals, Inc.

Protocol Number: BOS161721-02

SAP Version and Date: Version 3.0, 13Nov2020

[figure not shown]
CCI

Sponsor: Boston Pharmaceuticals, Inc.

Protocol Number: BOS161721-02

SAP Version and Date: Version 3.0, 13Nov2020

**CCI**

Sponsor: Boston Pharmaceuticals, Inc.

Protocol Number: BOS161721-02

SAP Version and Date: Version 3.0, 13Nov2020

**CCI**

**CCI**

**CCI**

## 13.9. C-SSRS

### 13.9.1. C-SSRS (Baseline/Screening)

| SUICIDAL IDEATION   |                              |  |                         |  |             |
|--|------------------------------|--|-------------------------|--|-------------|
| Ask questions 1 and 2. If both are negative, proceed to "Suicidal Behavior" section. If the answer to question 2 is "yes", ask questions 3, 4 and 5. If the answer to question 1 and/or 2 is "yes", complete "Intensity of Ideation" section below.   |                              | Lifetime: Time He/She Felt Most Suicidal                 |                         | Past 12 Months   |             |
| 1. Wish to be Dead
Subject endorses thoughts about a wish to be dead or not alive anymore, or wish to fall asleep and not wake up.
Have you wished you were dead or wished you could go to sleep and not wake up?
If yes, describe:   |                              | Yes  No  |                         | Yes  No  |             |
| 2. Non-Specific Active Suicidal Thoughts
General non-specific thoughts of wanting to end one's life/commit suicide (e.g., "I've thought about killing myself") without thoughts of ways to kill oneself/associated methods, intent, or plan during the assessment period.
Have you actually had any thoughts of killing yourself?
If yes, describe:   |                              | Yes  No  |                         | Yes  No  |             |
| 3. Active Suicidal Ideation with Any Methods (Not Plan) without Intent to Act
Subject endorses thoughts of suicide and has thought of at least one method during the assessment period. This is different than a specific plan with time, place or method details worked out (e.g., thought of method to kill self but not a specific plan). Includes person who would say, "I thought about taking an overdose but I never made a specific plan as to when, where or how I would actually do it... and I would never go through with it."
Have you been thinking about how you might do this?
If yes, describe:  |                              | Yes  No  |                         | Yes  No  |             |
| 4. Active Suicidal Ideation with Some Intent to Act, without Specific Plan
Active suicidal thoughts of killing oneself and subject reports having some intent to act on such thoughts , as opposed to "I have the thoughts but I definitely will not do anything about them."
Have you had these thoughts and had some intention of acting on them?
If yes, describe:  |                              | Yes  No  |                         | Yes  No  |             |
| 5. Active Suicidal Ideation with Specific Plan and Intent
Thoughts of killing oneself with details of plan fully or partially worked out and subject has some intent to carry it out.
Have you started to work out or worked out the details of how to kill yourself? Do you intend to carry out this plan?
If yes, describe:   |                              | Yes  No  |                         | Yes  No  |             |
| INTENSITY OF IDEATION   |                              |  |                         |  |             |
| The following features should be rated with respect to the most severe type of ideation (i.e., 1-5 from above, with 1 being the least severe and 5 being the most severe). Ask about time he/she was feeling the most suicidal.   |                              |  |                         | Most Severe  | Most Severe |
| Lifetime -  | Most Severe Ideation: | Type # (1-5)   | Description of Ideation |  |             |
| Past 12 Months -  | Most Severe Ideation: | Type # (1-5)   | Description of Ideation |  |             |
| Frequency   |                              |  |                         |  |             |
| How many times have you had these thoughts?
(1) Less than once a week (2) Once a week (3) 2-5 times in week (4) Daily or almost daily (5) Many times each day  |                              |  |                         |  |             |
| Duration  |                              |  |                         |  |             |
| When you have the thoughts how long do they last?
(1) Fleeting - few seconds or minutes (4) 4-8 hours/most of day
(2) Less than 1 hour/some of the time (5) More than 8 hours/persistent or continuous
(3) 1-4 hours/a lot of time   |                              |  |                         |  |             |
| Controllability   |                              |  |                         |  |             |
| Could/can you stop thinking about killing yourself or wanting to die if you want to?
(1) Easily able to control thoughts (4) Can control thoughts with a lot of difficulty
(2) Can control thoughts with little difficulty (5) Unable to control thoughts
(3) Can control thoughts with some difficulty (0) Does not attempt to control thoughts   |                              |  |                         |  |             |
| Deterrents  |                              |  |                         |  |             |
| Are there things - anyone or anything (e.g., family, religion, pain of death) - that stopped you from wanting to die or acting on thoughts of committing suicide?
(1) Deterrents definitely stopped you from attempting suicide (4) Deterrents most likely did not stop you
(2) Deterrents probably stopped you (5) Deterrents definitely did not stop you
(3) Uncertain that deterrents stopped you (0) Does not apply  |                              |  |                         |  |             |
| Reasons for Ideation  |                              |  |                         |  |             |
| What sort of reasons did you have for thinking about wanting to die or killing yourself? Was it to end the pain or stop the way you were feeling (in other words you couldn't go on living with this pain or how you were feeling) or was it to get attention, revenge or a reaction from others? Or both?
(1) Completely to get attention, revenge or a reaction from others (4) Mostly to end or stop the pain (you couldn't go on living with the pain or how you were feeling)
(2) Mostly to get attention, revenge or a reaction from others (5) Completely to end or stop the pain (you couldn't go on living with the pain or how you were feeling)
(3) Equally to get attention, revenge or a reaction from others and to end/stop the pain (0) Does not apply |                              |  |                         |  |             |

| SUICIDAL BEHAVIOR
(Check all that apply, so long as these are separate events; must ask about all types)   |  | Lifetime   | Past 1 Year  |
|--|--|---|---|
| Actual Attempt:
A potentially self-injurious act committed with at least some wish to die, as a result of act. Behavior was in part thought of as method to kill oneself. Intent does not have to be 100%. If there is any intent/desire to die associated with the act, then it can be considered an actual suicide attempt. There does not have to be any injury or harm , just the potential for injury or harm. If person pulls trigger while gun is in mouth but gun is broken so no injury results, this is considered an attempt.
Inferring Intent: Even if an individual denies intent/wish to die, it may be inferred clinically from the behavior or circumstances. For example, a highly lethal act that is clearly not an accident so no other intent but suicide can be inferred (e.g., gunshot to head, jumping from window of a high floor/story). Also, if someone denies intent to die, but they thought that what they did could be lethal, intent may be inferred.
Have you made a suicide attempt?
Have you done anything to harm yourself?
Have you done anything dangerous where you could have died?
What did you do?
Did you _____ as a way to end your life?
Did you want to die (even little) when you _____?
Were you trying to end your life when you _____?
Or did you think it was possible you could have died from _____?
Or did you do it purely for other reasons / without ANY intention of killing yourself (like to relieve stress, feel better, get sympathy, or get something else to happen)? (Self-Injurious Behavior without suicidal intent)
If yes, describe: |  |  Yes
 No |  Yes
 No |
|  |  | Total # of Attempts   | Total # of Attempts   |
| Has subject engaged in Non-Suicidal Self-Injurious Behavior?
Interrupted Attempt:
When the person is interrupted (by an outside circumstance) from starting the potentially self-injurious act (if not for that, actual attempt would have occurred).
Overdose: Person has pills in hand but is stopped from ingesting. Once they ingest any pills, this becomes an attempt rather than an interrupted attempt. Shooting: Person has gun pointed toward self, gun is taken away by someone else, or is somehow prevented from pulling trigger. Once they pull the trigger, even if the gun fails to fire, it is an attempt. Jumping: Person is poised to jump, is grabbed and taken down from ledge. Hanging: Person has noose around neck but has not yet started to hang - is stopped from doing so.
Has there been a time when you started to do something to end your life but someone or something stopped you before you actually did anything?
If yes, describe:  |  |  Yes
 No |  Yes
 No |
|  |  | Total # of interrupted                                      | Total # of interrupted                                      |
| Aborted Attempt:
When person begins to take steps toward making a suicide attempt, but stops themselves before they actually have engaged in any self-destructive behavior. Examples are similar to interrupted attempts, except that the individual stops him/herself, instead of being stopped by something else.
Has there been a time when you started to do something to try to end your life but you stopped yourself before you actually did anything?
If yes, describe:   |  |  Yes
 No |  Yes
 No |
|  |  | Total # of aborted  | Total # of aborted  |
| Preparatory Acts or Behavior:
Acts or preparation towards imminently making a suicide attempt. This can include anything beyond a verbalization or thought, such as assembling a specific method (e.g., buying pills, purchasing a gun) or preparing for one's death by suicide (e.g., giving things away, writing a suicide note).
Have you taken any steps towards making a suicide attempt or preparing to kill yourself (such as collecting pills, getting a gun, giving valuables away or writing a suicide note)?
If yes, describe:   |  |  Yes
 No |  Yes
 No |
| Suicidal Behavior:
Suicidal behavior was present during the assessment period?   |  |  Yes
 No |  Yes
 No |
| Answer for Actual Attempts Only   |  | Most Recent Attempt Date:                                   | Most Lethal Attempt Date:                                   |
| Actual Lethality/Medical Damage:
0. No physical damage or very minor physical damage (e.g., surface scratches).
1. Minor physical damage (e.g., lethargic speech; first-degree burns; mild bleeding; sprains).
2. Moderate physical damage; medical attention needed (e.g., conscious but sleepy, somewhat responsive; second-degree burns; bleeding of major vessel).
3. Moderately severe physical damage; medical hospitalization and likely intensive care required (e.g., comatose with reflexes intact; third-degree burns less than 20% of body; extensive blood loss but can recover; major fractures).
4. Severe physical damage; medical hospitalization with intensive care required (e.g., comatose without reflexes; third-degree burns over 20% of body; extensive blood loss with unstable vital signs; major damage to a vital area).
5. Death  |  | Enter Code  | Enter Code  |
| Potential Lethality: Only Answer if Actual Lethality=0
Likely lethality of actual attempt if no medical damage (the following examples, while having no actual medical damage, had potential for very serious lethality: put gun in mouth and pulled the trigger but gun fails to fire so no medical damage; laying on train tracks with oncoming train but pulled away before run over).  |  | Enter Code  | Enter Code  |
| 0 = Behavior not likely to result in injury
1 = Behavior likely to result in injury but not likely to cause death
2 = Behavior likely to result in death despite available medical care  |  | Enter Code  | Enter Code  |

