### 10.3. Other Safety Evaluations

#### 10.3.1. Columbia-Suicide Severity Rating Scale (C-SSRS)

The C-SSRS is a low-burden measure of the spectrum of suicidal ideation and behavior that was developed by Columbia University researchers for the National Institute of Mental Health Treatment of Adolescent Suicide Attempters Study to assess severity and track suicidal events through any treatment. It is a clinical interview providing a summary of both ideation and behavior that can be administered during any evaluation or risk assessment to identify the level and type of suicidality present. The C-SSRS can also be used during treatment to monitor for clinical worsening.i The C-SSRS evaluation will be performed as specified in the protocol Schedule of Assessments.

The C-SSRS has 11 binary (yes/no) outcomes corresponding to five categories of suicidal ideation, five categories of suicidal behavior, and the category of self-injurious behavior without suicidal intent:

Suicidal ideation is present if there is a “yes” response to any of the 5 suicidal ideation category questions. Suicidal behavior is present if there is a “yes” response to any of the 5 suicidal behavior category questions. Suicidal ideation or behavior is present if there is a “yes” response to any of the 10 suicidal or ideation or behavior category questions.

Sponsor: Boston Pharmaceuticals, Inc.  
Protocol Number: BOS161721-02  
SAP Version and Date: Version 3.0, 13Nov2020

The number and percentage of patients with any post-baseline occurrence of the following ideations and behaviors will be presented overall, by study phase and treatment group:

- Suicidal ideation (overall and by individual question),
- Suicidal behavior (overall and by individual question),
- Suicidal ideation or behavior,

A similar tabulation of the occurrence of any of the above ideations and behaviors at baseline or as part of their lifetime history/past 12-month history (collected at the screening visit) will be presented overall, by study phase, and treatment group.

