A shift table displaying the shift from worst pre-treatment category to the worst post-baseline category will be presented overall, by study phase, and treatment group. Best to worst C-SSRS category is defined in the following order: no suicidal ideation or behavior, suicidal ideation, and suicidal behavior. The worst post-baseline shift is calculated based on all post-baseline visits, including unscheduled visits. Worst pre-treatment will include all C-SSRS assessments prior to first dose date/time (screening or baseline). The denominator will be the number of patients with at least one non-missing baseline and post-baseline C-SSRS assessment.

Missing data will not be imputed.

All C-SSRS individual items will be presented in data listings for screening and post-screening (since last visit), separately. A separate listing will be presented for patients with suicidal ideation, suicidal behavior, or non-suicidal self-injurious behavior for all randomized patients.

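### The C-SSRS shift table treats all suicidal ideation as one category, so no summary counts patients whose ideation rose above their own pre-treatment level

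*SAP*

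**What the plan says.** SAP v3.0 Section 10.3.1 introduces the instrument with the remark that "The C-SSRS can also be used during treatment to monitor for clinical worsening". It then plans four kinds of output:

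- Counts and percentages of patients with any post-baseline ideation (overall and question by question), any behavior (likewise), and either, by study phase and treatment group.
- A matching tabulation for baseline and for the lifetime or past-12-month history taken at screening.
- "A shift table displaying the shift from worst pre-treatment category to the worst post-baseline category", by study phase and treatment group.
- By-patient listings of all items, plus a listing restricted to patients with ideation, behavior or non-suicidal self-injury.

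For the shift table, "Best to worst C-SSRS category is defined in the following order: no suicidal ideation or behavior, suicidal ideation, and suicidal behavior". Ideation counts as present on a yes "response to any of the 5 suicidal ideation category questions", with no grading among the five. On the pre-treatment side, "Worst pre-treatment will include all C-SSRS assessments prior to first dose date/time (screening or baseline").

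The form in Appendix 13.9.1 does grade the five questions. Intensity is rated for "the most severe type of ideation (i.e., 1-5 from above, with 1 being the least severe and 5 being the most severe"). Type 1 is the item where the "Subject endorses thoughts about a wish to be dead or not alive anymore". Type 5 is "Active Suicidal Ideation with Specific Plan and Intent", and it belongs to the ideation section, not the behavior section. The Since Last Visit form in Appendix 13.9.2 uses the same ranking.

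**The concern.** A shift table exists to show change within a patient. Here the category most likely to hold patients with some pre-treatment history covers everything from a passive wish to a plan with intent. Once a patient without behavior has answered yes to any ideation question before first dose, the table can register worsening only if suicidal behavior follows. A rise from type 1 to type 5 is tabulated exactly like no change, and exactly like a fall from type 5 to type 1.

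The same SAP keeps ordered severity in its other safety shifts. Section 10.2 shifts laboratory values from baseline to the worst CTCAE grade, and Section 10.3.3 shifts ECG results across ordered evaluations. Section 10.3.1 gives no reason for collapsing the ranking here. What is at stake is a descriptive safety summary. The primary endpoint, the significance level and power are not touched.

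**Working it through.** The SAP gives no figure to reproduce. The check applies its category rule to the form's own ranking.

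**Inputs.** Three shift categories and the any-of-five rule for ideation (Section 10.3.1); ideation types ranked 1 to 5 (Appendices 13.9.1 and 13.9.2).

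**Step 1: the single patient.** Worst pre-treatment answer: question 1 only, no behavior, so the category is ideation. Worst post-baseline answer: question 5, no behavior, so the category is again ideation. The patient falls in the ideation/ideation cell, on the diagonal.

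**Step 2: count the possible worsening moves.** Placing none below the five ideation types and behavior above them gives 1 + 5 + 1 = 7 ordered states. Possible worsening moves: 7 × 6 / 2 = 21.

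| Move | Possible | Visible with three categories |
|---|---|---|
| None to ideation types 1-5 | 5 | 5 |
| None to behavior | 1 | 1 |
| Ideation types 1-5 to behavior | 5 | 5 |
| Within ideation: 5 × 4 / 2 | 10 | 0 |
| Total | 21 | 11 |

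**Step 3: what the ideation/ideation cell mixes.** It pools 5 × 5 = 25 combinations of pre-treatment and post-baseline type: 10 worse, 5 unchanged, 10 better.

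**Step 4: effect of a finer split.**

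- Types 1-3 and 4-5 as separate categories: hidden moves are 3 × 2 / 2 = 3 within types 1-3 and 2 × 1 / 2 = 1 within types 4-5, together 4. The table then shows 21 − 4 = 17.
- All five types kept: hidden moves 0.

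**Step 5: whether the by-question tables recover the lost link.** Take two hypothetical arms of two patients each, and assume patients at a given type give the same answers. In arm X one patient goes from type 1 to type 5 and the other from type 5 to type 1. In arm Y one patient stays at type 1 and the other at type 5. Before dosing, both arms have one patient at each type; after dosing, the same. The by-question tables agree, and the three-category shift table puts both patients of each arm in the ideation/ideation cell. Yet one patient in arm X escalated and none in arm Y did. Separate before and after counts cannot recover this.

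**The case against.** The strongest reply is that the serious levels are already reported by arm. The by-question table in Section 10.3.1 counts patients with a post-baseline yes to question 4 (some intent) and question 5 (plan and intent) in each treatment group, whatever their history. In a randomized trial that is a valid between-arm comparison. This stands. A reader might infer from the shift table that escalation to intent or plan cannot be compared between arms, or that it is left to the listings alone. The SAP does not support that. On-study intent or plan is tabulated by arm; only the within-patient rise is not.

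Further points for the defence:

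- The sentence about monitoring clinical worsening describes what the instrument can do. It does not promise that the shift table will grade ideation. Correct, so the three categories contradict nothing in the SAP. The point is a weak choice, not an error.
- The SAP's reference list includes a C-SSRS scoring and analysis guide, which is not at hand. Whether three categories follow or depart from it cannot be judged and is not part of this point.
- No data are lost, since every item is listed. True, but screening and post-screening answers are listed separately, so a reader must match patients by hand.
- A finer table does not help if lifetime answers set the pre-treatment level, because a patient with remote type 5 ideation or behavior could then never show a rise within ideation. This also stands, and it is why the fix must name the look-back.

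**Conclusion.** The point holds in a limited form. The only planned within-patient C-SSRS comparison cannot show worsening inside ideation, and no other summary gives the number per arm who rose above their own pre-treatment ideation level.

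The 10 hidden moves out of 21 must not be read as a share of patients or events, although a reader might take it so. Each possible move counts once, and the SAP gives no rate of pre-treatment ideation from which to project patients. The number affected could be very small.

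The conclusion assumes that the table is built as Section 10.3.1 reads. The mock shells are a separate document and are not at hand; if they already split ideation, the text should say so. The type 1 to type 5 example assumes no suicidal behavior at any time and only question 1 positive before first dose. The gap within ideation remains under either look-back. The change is worth making because it concerns suicidality and costs little, but nothing inferential depends on it.

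**What to change.** In Section 10.3.1:

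1. Keep the three-category shift table.
2. Add a shift with at least four ordered categories: none, ideation types 1-3, ideation types 4-5, behavior. Keeping types 1 to 5 separate gives seven. Use the maximum category before first dose and the maximum post-baseline category.
3. Add one row per arm, on the shift-table denominator, for the number and percentage of patients whose maximum post-baseline category is worse than their maximum pre-treatment category.
4. State whether the lifetime or the past-12-month answers on the screening form define the pre-treatment maximum.

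No new data are needed, since both forms already record the ideation type. The cost is a few sentences in the SAP, an updated shell, and a larger table with many sparse cells: 4 × 4 = 16 per arm with four categories, or 7 × 7 = 49 with seven, against 3 × 3 = 9 now. Sparse cells are tolerable in a descriptive table, and the single row of worsened patients carries the between-arm comparison.
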